### **2.3.1.3 Risks of Experimental Infection with *N. americanus* Larval Inoculum**

Expected adverse effects of being inoculated with *N. americanus* infective larvae are local skin reactions at the site of application of the larvae and gastrointestinal symptoms upon maturation of the parasites into adult hookworms in the small intestine of the host. Reported skin reactions include localized maculopapular or papulovesicular rash that may be significant and prolonged (up to a month) when higher doses ( $\geq 50$ ) of larvae are applied. Occasional respiratory symptoms may be experienced during the migration of larvae through the lungs, including dry cough, shortness of breath, and wheeze. Reported gastrointestinal symptoms include abdominal bloating and pain, flatulence, diarrhea, nausea, and vomiting.

As with any investigational product, there is a theoretical possibility of risks of CHHI about which we have no present knowledge. Subjects will be informed of any such risks should further data become available during the course of this or other clinical studies. Risks associated with chronic hookworm infection include iron deficiency, iron-deficiency anemia (associated with fatigue and malaise) and chronic gastrointestinal symptoms including flatulence, abdominal bloating, abdominal pain, diarrhea, nausea, and vomiting. However, these usually only occur after several months or years of infection, which will not occur during this study.

Volunteers in this study who are experimentally infected with the *N. americanus* Larval Inoculum may develop patent infections and shed hookworm eggs in their feces. It is extremely unlikely that a bystander individual – for example, someone living in the same household as the study subject – could become infected with *N. americanus* due to exposure to these hookworm eggs that are shed, for several reasons. First, to become infectious to humans, hookworm eggs must hatch to release larvae into the environment. Hatching and development into infective larvae require a moist and warm environment (optimally between 23-33°C) and a certain period of time, generally estimated to be at least a week. Second, *N. americanus* larvae can infect humans only by coming into contact with skin; they are not infectious by oral ingestion.

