### 9.2.2 Vaccine Reactogenicity

All subjects will be observed for at least 60 minutes after each study vaccination to detect and treat any immediate AEs. Subjects will also complete study memory aids after each vaccination beginning with the day of vaccination and through 14 days after vaccination. Injection site reactions including bruising, redness, induration (hardness)/swelling, pain, and tenderness will be recorded on the study aids. Systemic reactions including fever, myalgia (body aches/muscular pains exclusive of the injection site), arthralgia (joint pains exclusive of the injection site), headache, nausea, and vomiting will also be recorded.

Subjects will also be asked to record any medications taken and any emergency room or healthcare provider visits (other than routine check-ups). The subject memory aid will be reviewed with the subject at subsequent clinic visits.

Vaccine reactogenicity events are AEs that are known to occur with types of vaccine similar in composition to those being tested in this study. The following Toxicity Grading Scales will be used to grade solicited local (injection site) and systemic (subjective and quantitative) reactions:

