**Table 1: Assessment of Solicited or Expected Adverse Event Severity – Vaccination Phase**

Adverse Event	Grade	Severity
Pain at injection site	1	Aware of pain but it does not interfere with daily activity and no pain medication is taken
	2	Aware of pain; there is interference with daily activity or it requires use of pain medication
	3	Aware of pain and it prevents daily activity
Tenderness at injection site	1	Area immediately surrounding injection site hurts only when touched or with arm motion, and it does not interfere with daily activity
	2	Area immediately surrounding injection site hurts when touched or with arm motion, and it interferes with daily activity
	3	Area immediately surrounding injection site hurts when touched or with arm motion, and it prevents daily activity
Erythema at injection site	1	25 mm – 50 mm
	2	51 mm – 100 mm
	3	> 100 mm
Induration/swelling at injection site	1	25 mm – 50 mm and does not interfere with daily activity
	2	51 mm – 100 mm or interferes with daily activity
	3	>100 mm or prevents daily activity
Fever* (oral†)	1	38.0°C – 38.4°C
	2	38.5°C – 38.9°C
	3	>39.0°C
Headache	1	Easily tolerated, does not interfere with daily activity
	2	Repeated use of non-narcotic pain reliever for >24 hours or interferes with daily activity
	3	Any use of narcotic pain reliever or prevents daily activity

Nausea	1	Easily tolerated, does not interfere with daily activity
	2	Interferes with daily activity
	3	Prevents daily activity
Vomiting	1	1-2 episodes in 24 hours and does not interfere with activity
	2	> 2 episodes in 24 hours or interferes with daily activity
	3	Prevents daily activity or requires outpatient IV hydration
Myalgia**	1	Easily tolerated, does not interfere with daily activity
	2	Interferes with daily activity
	3	Prevents daily activity
Arthralgia**	1	Easily tolerated, does not interfere with activity
	2	Interferes with daily activity
	3	Prevents daily activity

\* Oral temperature assessed on Day 0 (Visit 1) prior to the first study vaccination will be considered as baseline. Temperatures obtained during the clinic visits will be recorded.

† Subjects must not eat or drink anything hot or cold, or smoke within 10 minutes prior to taking oral temperature.

\*\* Not at injection site.

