### 9.2.3 CHHI Reactogenicity

All subjects will be observed for at least 60 minutes after application of the *N. americanus* larvae during CHHI to detect and treat any immediate AEs. Subjects will also complete study memory aids after CHHI beginning with the day of larval application and through Day 280 when they will be treated with albendazole to cure their infections. For the first 4 weeks after application of the *N. americanus* Larval Inoculum, the memory aids will be used to record pruritus, pain, tenderness, rash and swelling at the site of larval application, as well as cough and sore throat (to capture symptoms that may possibly be related to larval migration through the lungs). Starting on Day 175 (approximately 5 weeks after CHHI) of the study until the participant receives their first dose of albendazole, the memory aids will be used to record nausea, vomiting, diarrhea, abdominal pain, abdominal bloating and flatulence. Female participants of childbearing potential will additionally capture on the memory aids the form of contraception they are using. The memory aids will include a printed reminder of the potential risks associated with use of albendazole during pregnancy.

Subjects will also be asked to record any medications taken and any emergency room or healthcare provider visits (other than routine check-ups) through Day 297. The subject memory aid will be reviewed with the subject at subsequent clinic visits.

CHHI reactogenicity events are AEs that are known to occur with hookworm infection. The following Toxicity Grading Scales will be used to grade solicited local (larval application site) and systemic (subjective and quantitative) reactions:

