**Table 3: Assessment of Solicited or Expected Adverse Event Severity – CHHI Phase**

Adverse Event	Grade	Severity
Pain at site of larval application	1	Aware of pain but it does not interfere with daily activity and no pain medication is taken
	2	Aware of pain; there is interference with daily activity or it requires use of pain medication
	3	Aware of pain and it prevents daily activity
Tenderness at site of larval application	1	Area immediately surrounding application site hurts only when touched or with arm motion, and it does not interfere with daily activity
	2	Area immediately surrounding application site hurts when touched or with arm motion, and it interferes with daily activity
	3	Area immediately surrounding application site hurts when touched or with arm motion, and it prevents daily activity
Rash at site of larval application	1	25 mm – 50 mm and does not interfere with daily activity
	2	51 mm – 100 mm or interferes with daily activity
	3	> 100 mm or prevents daily activity
Induration/swelling at site of larval application	1	25 mm – 50 mm and does not interfere with daily activity
	2	51 mm – 100 mm or interferes with daily activity
	3	> 100 mm or prevents daily activity
Pruritus at site of larval application	1	Easily tolerated, does not interfere with daily activity
	2	Interferes with daily activity
	3	Prevents daily activity
Abdominal pain	1	Easily tolerated, does not interfere with daily activity
	2	Interferes with daily activity
	3	Prevents daily activity
Abdominal bloating	1	Easily tolerated, does not interfere with activity
	2	Interferes with daily activity
	3	Prevents daily activity
Nausea	1	Easily tolerated, does not interfere with daily activity
	2	Interferes with daily activity
	3	Prevents daily activity
Vomiting	1	1-2 episodes in 24 hours and does not interfere with activity
	2	> 2 episodes in 24 hours or interferes with daily activity
	3	Prevents daily activity or requires outpatient IV hydration
Diarrhea	1	2-3 loose stools/24 hours
	2	4-5 stools/24 hours
	3	> 6 loose stools or requires outpatient IV hydration
Flatulence	1	Easily tolerated, does not interfere with daily activity
	2	Interferes with daily activity
	3	Prevents daily activity
Cough	1	Easily tolerated, does not interfere with daily activity
	2	Interferes with daily activity
	3	Prevents daily activity
Sore throat	1	Easily tolerated, does not interfere with daily activity
	2	Interferes with daily activity

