## **9.5 Halting Rules**

If the study vaccine or CHHI is considered significantly reactogenic or results in significant AEs (see below and **Section 9.2**), additional vaccinations or CHHIs will be suspended until reviewed by the SMC, Independent Safety Monitor, DMID Medical Monitor, and IND sponsor (BCM). Any recommendation of the Independent Safety Monitor, DMID Medical Monitor, and SMC to resume or suspend further injections or CHHIs (either for an individual subject or the full study) will be communicated in writing to the sponsor and Principal Investigator. All communications from the SMC will subsequently be forwarded by the investigators to the IRB.

The following criteria will be used to define significant reactogenicity:

- One or more participants experience a protocol defined SAE that is determined to be possibly, probably, or definitely related to a study vaccine or CHHI, **OR**,
- One or more participants experience a protocol defined AESI that is determined to be possibly, probably, or definitely related to a study vaccine or CHHI, **OR**,
- One or more participants experience a protocol defined Grade 3 hypersensitivity reaction that is possibly, probably or definitely related to a study vaccine or CHHI, **OR**,
- Two or more participants experience a protocol defined Grade 2 hypersensitivity reaction that is probably or definitely related to a study vaccine or CHHI, **OR**,
- Three or more participants experience the same objective physical finding or laboratory abnormality of Grade 3 or higher (with the exception of isolated Grade 3 erythema or swelling at the site of vaccination or Grade 3 erythema and/or rash at the site of application of the larvae), that is determined to be probably or definitely related to a study vaccine or CHHI, **OR**,
- Three or more participants experience the same Grade 2 or higher safety laboratory abnormality (excluding eosinophilia [or increased white blood cell count secondary to eosinophilia] after CHHI) or Grade 3 clinical AE that is possibly, probably or definitely related to a study vaccine or CHHI.

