- c. The proportion of subjects with detectable hookworm eggs in each of the intervention groups (Groups 1, 2 and 3) will be compared to the proportion of subjects in the placebo control group (Group 4) using a one sided Fisher exact test. The p-values from the three tests will be adjusted using the Holm-Bonferroni procedure to control the familywise error rate at 0.05. Power calculations are based on this outcome.

Primary Objective #2: To evaluate the safety and reactogenicity of Na-GST-1/ Alhydrogel® delivered with or without AP 10-701 or CpG 10104 on Days 0, 56 and 112, in healthy, hookworm-naïve adults.

AEs will be coded according to Medical Dictionary of Regulatory Activities (MedDRA™) preferred terms. The frequency, severity, and relationship of AEs per each vaccine formulation of Na-GST-1 will be presented in tabular form using the MedDRA™ coded term and organized by MedDRA™ System, Organ, and Class (SOC) designations.

1. The frequency of solicited local injection site and systemic AEs, and unsolicited AEs will be summarized by SOC and preferred term.
2. Line listings of clinical and laboratory AEs classified as solicited injection site, solicited systemic, or unsolicited and will be displayed in tables stratified by formulation group (i.e., Na-GST-1/Alhydrogel, Na-GST-1/Alhydrogel plus AP 10-701, Na-GST-1/Alhydrogel plus CpG 10104, or saline placebo).
3. AEs will be summarized by severity and relationship to vaccine by individuals and formulation of Na-GST-1.
4. The frequency of vaccine-related SAEs and AESIs will be tallied as well as summarized by body system, by vaccine formulation.

*Primary Outcome #2 Measures:*

The following summary parameters will be evaluated for each formulation of Na-GST-1, in comparison to saline placebo control:

1. Frequency of solicited injection site and systemic reactogenicity, graded by severity, on the day of each study vaccination through 14 days after each study vaccination.
2. Frequency of solicited adverse events, graded by severity, on the day of CHHI through study Day 280.
3. Frequency of study vaccine-related Serious Adverse Events from the time of the first study vaccination through approximately 10 months after the last study vaccination.
4. Frequency of clinical safety laboratory adverse events.

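### The Grade 3 limit for raised WBC in Protocol Table 5 points the wrong way, and halting criterion 6 captures the Grade 3 site reactions that criterion 5 exempts

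*Protocol*

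**What the plan says.** **Raised WBC.** The row for WBC increase in Protocol Table 5 gives Grade 1 as 10,800–15,000/mm³, Grade 2 as 15,001–20,000/mm³ and Grade 3 as <20,000/mm³. Section 5.3.3 lets dose 2, dose 3 or the CHHI be withheld when a Grade 3 laboratory value has not come down to Grade 2 or lower.

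**Halting rules.** Section 9.5 lists six unnumbered criteria joined by OR. I call the fifth and sixth bullets criteria 5 and 6.

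- Criterion 5 applies to three participants with the same Grade 3 objective finding or laboratory abnormality, at least probably related, "with the exception of isolated Grade 3 erythema or swelling at the site of vaccination or Grade 3 erythema and/or rash" at the larval application site.
- Criterion 6 applies to three participants with the same laboratory abnormality of Grade 2 or above, "or Grade 3 clinical AE that is possibly, probably or definitely related to a study vaccine or CHHI". Its only exclusion is eosinophilia after CHHI, or a WBC rise secondary to it, and that sits in the laboratory limb.

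**Whether site reactions are AEs.** Section 9.2.2 says "Vaccine reactogenicity events are AEs that are known to occur with types of vaccine similar in composition" to those under test, and section 9.2.3 says "CHHI reactogenicity events are AEs that are known to occur with hookworm infection". Section 11.4 plans "Line listings of clinical and laboratory AEs classified as solicited injection site, solicited systemic, or unsolicited". Table 1 grades "Erythema at injection site" and Table 3 grades "Rash at site of larval application", each up to Grade 3.

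**The concern.** A safety grading table and a set of halting rules should give one answer to whoever applies them. Here each can give an unintended one.

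The WBC limit is the part that errs against safety. A marked leukocytosis is the value the Grade 3 cell exists to catch. As printed, it falls outside the cell, and therefore outside every rule that refers to the grade.

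The halting overlap errs the other way. Criterion 5 exempts certain site reactions, yet three cases of one of them would still suspend vaccinations or CHHIs under criterion 6. The suspension lasts until the SMC, Independent Safety Monitor, DMID Medical Monitor and IND sponsor have reviewed it. Dose 2, dose 3 and the CHHI each have a ±7-day window in Appendix A. A long enough review would push due subjects out of window and into the sponsor-approval route of section 6.3. The exempted reactions are also expected ones: section 2.3.1.3 describes "rash that may be significant and prolonged (up to a month) when higher doses" of 50 or more larvae are applied, and this trial applies 50.

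**Working it through.** No stated power or sample-size figure bears on this point. The check is to apply the printed rules and see what they return.

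**1. WBC grades, printed and corrected (Table 5).**

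| Count per mm³ | Grades met as printed | Grade with >20,000 |
|---|---|---|
| 7,000 | 3 | none |
| 12,000 | 1 and 3 | 1 |
| 18,000 | 2 and 3 | 2 |
| 20,000 | 2 | 2 |
| 25,000 | none | 3 |

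The eosinophil-increase row of the same table ends correctly in >5000/mm³. A less-than sign suits only the rows for decreases, such as WBC decrease, which ends in <1400/mm³.

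**2. Where the WBC limit is used.** Take a count of 25,000, which has no printed Table 5 grade.

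- Criterion 5 needs Grade 3, so it is not met.
- Criterion 6 needs Grade 2 or above, so it is not met.
- The section 5.3.3 rule needs a Grade 3 value, so it is not met.

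With >20,000 the count is Grade 3 and comes within the scope of all three rules. Criterion 6 still excludes a rise secondary to eosinophilia after CHHI.

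**3. The two halting criteria side by side (section 9.5).**

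| | Criterion 5 | Criterion 6, clinical limb |
|---|---|---|
| Participants | 3 or more | 3 or more |
| Grade | 3 | 3 |
| Relatedness | at least probable | at least possible |
| Site-reaction exemption | yes | none |

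**4. Does the exemption change any outcome?** Take three participants with one of the 3 exempted reactions (vaccination-site erythema, vaccination-site swelling, larval-site rash), at Grade 3 and at each of 3 relatedness levels (possible, probable, definite). That is 3 × 3 = 9 combinations.

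- As written: criterion 5 fires in 0 of 9 and criterion 6 in 9 of 9.
- If the exemption were deleted from criterion 5: criterion 5 would fire in 3 × 2 = 6 (probable and definite). All 6 already halt under criterion 6, so no outcome changes.
- If the exemption were repeated in criterion 6: 0 of 9 halt.

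**5. Scope.** Table 1 grades 4 vaccination-site reactions (pain, tenderness, erythema, induration/swelling). Table 3 grades 5 larval-site reactions (pain, tenderness, rash, induration/swelling, pruritus). The total is 4 + 5 = 9. Criterion 5 exempts 2 + 1 = 3, and criterion 6 exempts 0. With the exemption repeated, 9 − 3 = 6 would still count towards a halt.

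**The case against.** **Clinical AE is not defined.** One could read criterion 5 as the specific rule for measured findings such as erythema, swelling and rash, and leave criterion 6 for other clinical events. Both clauses would then have effect. It is fair that the term is undefined and that section 11.4 describes listings, not halting. But no passage states the narrower meaning. Sections 9.2.2 and 9.2.3 call these reactions AEs, and OR makes criterion 6 sufficient alone. If the narrower meaning was intended, the added clause merely records it.

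**Criterion 6 may be a deliberate catch-all.** Deleting the exemption from criterion 5 would also remove the inconsistency, and copying it loosens a safety rule. The documents do not exclude this. However, it would leave no purpose for an exemption that the protocol spells out in detail.

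**The WBC sign is an obvious slip.** The row label and the first two grades leave only one sensible reading. Section 9.2.1 also gives a general severity scale, section 5.3.3 allows the investigator to withhold dosing for other reasons, and section 9.2.6 requires abnormal values to be followed. This stands as far as it goes. A reader might infer that a count above 20,000 would go unmanaged, and the documents do not support that. The printed threshold is still wrong.

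**The overlap has little consequence.** A reader might infer that expected larval-site rash would probably halt the trial. The documents do not support that either. Section 2.1.9.1 reports that Phase 1 skin reactions were mild or moderate in most cases. The description in section 2.3.1.3 is not a statement about Grade 3. No Grade 3 rate and no review time is given. A subject's rash follows that subject's own challenge, so a pause can delay only other subjects. The IND sponsor, already one of the reviewers, can approve late dosing.

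**There is a mirror gap.** Criterion 5 does not carry criterion 6's exclusion of eosinophilia. Three cases of Grade 3 eosinophilia after CHHI that are at least probably related would halt under criterion 5. That is correct. It supports rereading the two bullets together.

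**Conclusion.** Both items are wrong as written.

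The WBC limit is the more serious in direction, because as printed it takes counts above 20,000/mm³ out of two halting criteria and one dose-withholding rule. The probable harm is limited by clinical judgement and the other safeguards in the protocol.

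The halting overlap makes criterion 5's exemption inoperative for all 3 reactions it names. It costs an avoidable but reviewable suspension, not a permanent stop, and it changes no endpoint or error rate directly. Its frequency cannot be estimated: any probability would rest on an assumed Grade 3 rate.

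The conclusion rests on reading section 9.5 literally, on site reactions being clinical AEs as sections 9.2.2, 9.2.3 and 11.4 indicate, and on the exemption in criterion 5 being intended to have effect.

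**What to change.** 1. In Table 5, change the Grade 3 limit for WBC increase from <20,000/mm³ to >20,000/mm³.
2. In the clinical-AE limb of criterion 6 in section 9.5, repeat criterion 5's exemption with the same scope: isolated Grade 3 erythema or swelling at the vaccination site, and Grade 3 erythema and/or rash at the larval site. Leave the other site reactions counting.

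While the section is open, the sponsor could also state whether the eosinophilia exclusion in criterion 6 is meant to apply to criterion 5.

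The cost is a short protocol amendment through the IRB (section 15.6): one symbol and one repeated clause. It adds no procedures, visits or subjects.

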## 9.6 Unblinding

The study will be double-blinded until all study subjects have completed their final study visit. Prior to final study unblinding, a study subject's randomization code may be unblinded only for safety purposes. This is unlikely to occur, since once a vaccine is administered, knowing which vaccine was given is unlikely to influence the medical management of an AE. This procedure is therefore exceptional and any decision to unblind will be discussed with the sponsor, the Principal Investigator, the Independent Safety Monitor, and the SMC. If deemed necessary for urgent safety reasons, the Independent Safety Monitor, in consultation with the SMC (if possible in a timely manner), may unblind a specific subject without revealing the study blind to the investigators or the Sponsor. Any unblinding will be thoroughly documented. It is to be emphasized that the Independent Safety Monitor may put the study on hold at any time and discuss with the SMC. In the event that the investigators come to know the study code prior to final unblinding, the Principal Investigator must notify the Sponsor immediately. The reasons will be documented by the Principal Investigator and added to the study file.

The decision to completely unblind the study prior to the final study Day 380 visit or to permanently stop the study prior to Day 380 will take the form of a formal recommendation by the SMC to the study Sponsor. The Principal Investigator must then notify the IRB of this decision.

